6.3. Measures to Minimize Bias: Randomization and Blinding

To preserve the blinding of the study, a minimum number of Lilly personnel who are not directly involved with investigational sites will see the randomization table and treatment assignments before the study is complete.

Joint, disease activity, and safety assessments

Joint Assessor

To prevent potential bias due to observed efficacy or laboratory changes, a “dual assessor” approach will be used to evaluate efficacy and safety. The Joint Assessor (or designee) should be a rheumatologist or skilled arthritis assessor. The Joint Assessor will be responsible for completing the joint counts. To ensure consistent joint evaluation throughout the trial, individual participants should be evaluated by the same Joint Assessor for all study visits. The Joint Assessor must not access or discuss with the participant the patient-reported assessments, Physician’s Global Assessment of Disease Activity (PhGADA_VAS), and safety assessments.

Safety Assessor

The Safety Assessor (or designee) should be a rheumatologist (or medically qualified physician) and will have access to both safety and efficacy data. The Safety Assessor may be the principal investigator. The Safety Assessor will be responsible for completing the PhGADA_VAS. To ensure consistent PhGADA_VAS throughout the trial, the instrument should be evaluated by the same physician at all study visits. The Safety Assessor will have access to source documents, laboratory results, and electronic case report forms (eCRFs) and will be responsible for making treatment decisions based on a participant’s clinical response and laboratory parameters.

Method of treatment assignment

Assignment to treatment groups will be determined by a computer-generated random sequence using an interactive web-response system (IWRS).

Participants will be stratified by prior use of csDMARD only or by tsDMARD/bDMARDs use (yes versus no).

Emergency unblinding

In case of an emergency, the investigator has the sole responsibility for determining if unblinding of a participant's treatment assignment is warranted. Participant safety must always be the first consideration in making such a determination. If a participant's treatment assignment is unblinded, the sponsor must be notified immediately.

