4.1. General Considerations

The independent variable, previous RA therapy population, is defined as only csDMARD experienced or bDMARD/tsDMARD experienced participants. Unless otherwise indicated in the statistical analysis plan (SAP), the analyses will be conducted as follows:

Analysis for	Description
Primary and secondary endpoint analyses comparing LY3462817 to placebo	Tested at a 2-sided level of 0.05 for frequentist analyses
Adjustments for multiplicity	None to be performed
Baseline	Defined as the last available value before the first dose of study intervention for both efficacy and safety analyses. In most cases, this value will be what is recorded at the randomization visit (Visit 2).
Change from baseline	Will be calculated as the visit value of interest minus the baseline value.
Efficacy and patient-reported outcome (PRO) analysis	Analysis models may contain the independent variables such as treatment group, baseline disease activity, and previous RA therapy population. Endpoint analyses will use the FAS unless otherwise specified.
Dichotomous responder endpoints	Missing data will be imputed using the nonresponder imputation (NRI) method. Will be analyzed using a logistic regression model with treatment group, baseline disease activity, and previous RA therapy population as model covariates.
NRI analysis	Participants will be considered nonresponders if: 
 • they do not meet all the clinical response criteria • they are noncompliant with concomitant medication rules

	
 • they permanently discontinue study intervention at any time before the end of the treatment period for any reason, or • they are randomized and do not have at least 1 postbaseline observation.
Continuous efficacy endpoints	
Mixed-effects model for repeated measures (MMRM) will be used.
 
The MMRM model will include treatment, strata (previous RA therapy population), baseline value, visit, treatment-by-visit interaction in the model as fixed factors, and patient as a random factor.
 
An unstructured covariance matrix will be used to model the within-subject errors. If this analysis fails to converge, other structures will be tested (in this order: Toeplitz, Autoregressive with heterogeneity, and compound symmetry.).
 
The Kenward-Roger approximation will be used to estimate denominator degrees of freedom. Significance tests will be based on least squares means and Type III tests.

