4.4.1.2. Main analytical approach

4.4.1.2.1 ACR20

The frequency and percentage of patients achieving ACR20 response will be summarized by treatment arm at each post-baseline visit. A logistic regression model will be used to test the treatment difference of each LY dose versus placebo at each post-baseline visit with treatment group, baseline disease activity, and previous RA therapy population as model covariates. Baseline DAS28-CRP score will be used as the baseline variable. NRI as described in Section 4.1 will be used to impute missing data for ACR20 in patients who were Week 12 non-responders or who discontinued prior to Week 12.

The Kaplan-Meier estimator will be used to summarize time to ACR20 response over 12 weeks and a plot by treatment arm will be presented. Week 12 non-responders will be censored on the date of the Week 12 visit. All patients ongoing at Week 12 and who have not yet responded will be censored on the date of the Week 12 visit. A Cox proportional hazards model will be used to test the treatment comparison between each LY dose and placebo in time to ACR20 response over 12 weeks.

For participants who discontinue study intervention and/or receive rescue therapy, post-discontinuation or post-rescue observations will not be included.

Subjects with ACR20 response will also be listed.

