4.4.1.2.2 ACR50/70

ACR50 and ACR70 are calculated in the same manner as ACR20, but are based on 50% and 70% improvement, respectively.

Summaries and analyses similar to those described for ACR20 in Sections 16.1.3.1 will be conducted for ACR50 and ACR70.

Subjects with ACR50/70 response will also be listed.

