4.6.4.4. Immunogenicity

The frequency and percentage of patients with positive anti-drug antibodies (ADAs) by visit will be summarized by treatment arm. The frequency and percentage of patients with positive ADAs

at any time point during the Treatment Period (including pre-treatment visits) up to and including Visit 9 (Week 24) will also be summarized by treatment arm.

The frequency and percentage of patients with a treatment-emergent positive ADA incidence will be summarized by treatment arm. A treatment-emergent incidence is defined as a four-fold increase [2 dilution increase] in immunogenicity titer over the baseline titer during the Treatment Period. Scheduled visits, unscheduled visits, and repeat measurements will be included.

The time to the development of treatment-emergent ADAs will be calculated as:

Time to development of treatment-emergent ADAs (in weeks) = (Date of development of treatment-emergent ADAs – Date of randomization + 1) / 7.

If a patient has not developed treatment-emergent ADAs, they will be censored at the date of the last immunogenicity assessment during the Treatment Period. If they did not have an immunogenicity assessment, they will be censored at the date of first injection.

The time to development of treatment-emergent ADAs will be analyzed using a Cox proportional hazards model, with treatment arm and strata (previous RA therapy population) fitted as explanatory variables. The estimated hazard ratio, 95% confidence interval and p-value for treatment comparisons between each LY dose and placebo will be presented. A Kaplan-Meier plot of the time to development of treatment-emergent ADAs will be presented by treatment arm.

The frequency and percentage of patients with both a treatment-emergent positive ADA incidence (yes, no) and at least one treatment-emergent Hypersensitivity adverse event (yes, no) will be summarized by treatment arm. Similarly, the frequency and percentage of patients with both a treatment-emergent positive ADA incidence (yes, no) and at least one treatment-emergent injection site reaction (yes, no) adverse event will be summarized by treatment arm.

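### The Cox model for time to ACR20/50/70 response names only the treatment comparison; it should include previous RA therapy and baseline DAS28-CRP, as the logistic model for the same response does

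*SAP*

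**What the plan says.** SAP 4.4.1.2.1 analyses ACR20 response in two ways.

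- **Proportion responding:** logistic regression "with treatment group, baseline disease activity, and previous RA therapy population as model covariates". Baseline DAS28-CRP is named as the baseline variable.
- **Time to response over 12 weeks:** "A Cox proportional hazards model will be used to test the treatment comparison between each LY dose and placebo in time to ACR20 response". No covariate, stratum or method for ties is given.

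SAP 4.4.1.2.2 carries this forward: "Summaries and analyses similar to those described for ACR20 in Sections 16.1.3.1 will be conducted for ACR50 and ACR70". The section number cited there does not exist in this SAP, but the intention is clear. The gap therefore covers three response levels and two doses, or six tests.

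Previous RA therapy (csDMARD only, or tsDMARD/bDMARD use) is the randomisation stratum in Protocol 6.3. The general rule in SAP 4.1 is permissive: "Analysis models may contain the independent variables such as treatment group, baseline disease activity, and previous RA therapy population". The SAP's only other Cox model, for time to treatment-emergent antidrug antibodies (4.6.4.4), is specified "with treatment arm and strata (previous RA therapy population) fitted as explanatory variables".

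**The concern.** The same response is tested with two named covariates by logistic regression and, as written, with none by Cox regression. This is not the plan's usual practice. The primary MMRM (SAP 4.3.2), the remission and low-disease-activity logistic models (4.5.1 to 4.5.4), the MRI ANCOVA (4.5.5) and the subgroup MMRM (4.7.2) all name the stratum and a baseline value. Nor is it a convention for Cox models, since 4.6.4.4 names the stratum.

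Two things are at stake. First, SAP 4.1 allows adjustment without requiring it, so the covariates of this model are either absent or left to the analyst. Second, when an omitted covariate is prognostic, the Cox hazard ratio for treatment moves toward 1 relative to the conditional hazard ratio and the test loses power. With about 20 placebo participants there is little power to spare.

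**Working it through.** **The plan's own figure.** The documents give no hazard ratio, response rate, event count or power for time to ACR response. The only stated power is more than 80% for the primary endpoint (SAP 5), with means -1.80 and -0.75, SD 1.25, 40 versus 20 and two-sided alpha 0.05.

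- SE = 1.25 × √(1/20 + 1/40) = 0.342
- 1.05 / 0.342 = 3.07
- Power = Φ(3.07 − 1.96) = 86.6% by the normal approximation, or 85.5% by the noncentral t with 58 df

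The stated figure reproduces, and this point does not touch it.

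**Inputs for the Cox check.** From the documents: 40 (700 mg) versus 20 (placebo), stratified allocation, visits at Weeks 2, 4, 8 and 12, two-sided alpha 0.05. Assumed, because the documents give nothing: placebo 12-week response 30%, conditional hazard ratio 2.5, half of participants in each stratum, and the prognostic strengths in the table.

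**Model.** Hazard = λ × exp(ln 2.5 × treatment + ln HRs × stratum + ln HRb × standardised baseline), with λ = −ln(0.70)/12 = 0.0297 per week. Response is recorded at the next visit. Each data set was fitted twice, with treatment only and with treatment, stratum and baseline as explanatory variables (Efron ties, Wald test). There were about 1,500 runs per setting. The Monte Carlo SE of one power figure is about √(0.5 × 0.5/1500) = 1.3 points, and the two fits share data.

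**Hand check of the first row.**

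- Expected placebo events: 20 × 0.30 = 6
- Expected 700 mg events: 40 × (1 − 0.70^2.5) = 40 × 0.59 = 23.6
- SE of log hazard ratio ≈ √(1/6 + 1/23.6) = 0.457
- ln 2.5 / 0.457 = 2.00, so power ≈ Φ(0.04) = 52%, in line with the simulated 49.6%

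| Assumed prognostic strength | Median HR, unadjusted / adjusted | Power, unadjusted / adjusted | Power difference |
|---|---|---|---|
| None | 2.46 / 2.50 | 49.6% / 50.0% | 0.4 points |
| Weak: stratum 1.5, baseline 1.2 per SD | 2.50 / 2.57 | 52.0% / 53.4% | 1.4 points |
| Moderate: stratum 2, baseline 1.5 per SD | 2.31 / 2.51 | 45.9% / 53.7% | 7.8 points |
| Strong: stratum 3, baseline 2 per SD | 2.12 / 2.53 | 38.6% / 55.1% | 16.5 points |

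**Under the null (hazard ratio 1).** Across the settings, the unadjusted test rejected in 2.7% to 4.3% of runs and the adjusted test in 3.9% to 5.0%.

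**How the gain divides.** A separate simulation used a stratified Cox model with stratum HR 0.5 and baseline HR 0.61 per SD. Power was 42.6% with treatment only, 45.4% with stratification (+2.8) and 50.7% with baseline added (+5.3). With no baseline effect, stratification alone moved power from 49.3% to 52.5% (+3.2). At moderate strength, most of the gain therefore comes from the baseline score.

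**Not simulated:** 300 mg versus placebo (20 versus 20), and the lower response rates expected for ACR50 and ACR70.

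**The case against.** Much of the opposing case stands.

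- **A reader might infer that the hazard ratio is attenuated and power is lost as a matter of fact.** The documents do not support that, because they give no prognostic strength. ACR response is improvement relative to the participant's own baseline (Protocol 8.1.3), so baseline DAS28-CRP cannot be presumed prognostic. If neither factor is, nothing is lost.
- **A reader might infer that ignoring the stratum makes the test invalid.** It does not. The unadjusted test did not exceed 5% under the null in any setting, and it became conservative in the strongest one. The unadjusted hazard ratio also targets a marginal quantity, so part of the shift is non-collapsibility. Baseline DAS28-CRP is not a randomisation factor, and adjusting for it is an efficiency choice.
- **A reader might infer that a development decision rests on this test.** Nothing says so. The listed endpoints are proportions achieving ACR20/50/70 (Protocol 9.4.3, SAP 4.4.1.1), tested by the adjusted logistic model. The planned interim efficacy assessment uses DAS28-CRP (Protocol 9.5, SAP 4.8). Time to response is an unlisted, unpowered addition.
- **A reader might infer a large penalty from tied visit times.** That appears only if every response falls on one of four exact days. Visits carry a ±7-day window (Protocol 1.3) and the SAP censors on actual visit dates. In 400 runs of the unadjusted model, the gap between Breslow and Efron handling was 6.9 points with exact days (37.2% versus 44.1%), 0.6 with dates spread ±3 days (42.2% versus 42.8%) and 1.4 with ±7 days (38.8% versus 40.2%). The uniform spread is an assumption.
- **Adjustment is not free for rare responses.** If placebo ACR70 response were 5% (assumed), the chance of no placebo event is 0.95^20 = 36%; at 10% it is 0.90^20 = 12%. Extra terms make such fits more fragile.

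The permissive sentence in SAP 4.1 means that adjustment is not excluded, but it does not settle the model.

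**Conclusion.** The point holds as a conditional, minor one. The Cox model for time to ACR20, and by reference ACR50/70, omits the randomisation stratum and the baseline score that the adjacent logistic model uses. If these are prognostic, the omission pulls the hazard ratio toward 1 relative to the conditional value and loses power. The loss is about 0, 1, 8 or 16 points as prognostic strength goes from none to strong. Those figures rest on assumed inputs for 700 mg versus placebo and an ACR20-like response rate. In the settings tested, adjustment kept type I error at or below 5% and lost no power. The unadjusted test is valid and the primary analysis is unaffected.

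**What to change.** In SAP 4.4.1.2.1, replace the Cox sentence with, for example: *Time to ACR20 response over 12 weeks will be compared between each LY dose and placebo using a Cox proportional hazards model with treatment group, previous RA therapy population and baseline DAS28-CRP as explanatory variables.* This fits the stratum in the same way as 4.6.4.4 and matches the logistic model.

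In 4.4.1.2.2, correct the cross-reference to 4.4.1.2.1, apply the same model to ACR50 and ACR70, and state before unblinding that covariates will be dropped, and in what order, if events are too few for a stable fit. Naming Efron handling of ties is an optional clarification. If an unadjusted model is intended, the SAP should say so.

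The cost is a sentence or two in the SAP. Both variables are already collected and already used for the same response. The small downside is possible instability with few ACR70 events, which the fallback addresses.

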4.4.1.2.2 ACR50/70

ACR50 and ACR70 are calculated in the same manner as ACR20, but are based on 50% and 70% improvement, respectively.

Summaries and analyses similar to those described for ACR20 in Sections 16.1.3.1 will be conducted for ACR50 and ACR70.

Subjects with ACR50/70 response will also be listed.

4.4.1.2.3 Individual components of the ACR Core Set

The following individual components of the ACR Core Set will be summarized and provided as listing:

- TJC (68 joint count),
- SJC (66 joint count),
- Patient's Global Assessment of Arthritis Pain (VAS),
- Patient's Global Assessment of Disease Activity (PaGADA_VAS),
- Physician's Global Assessment of Disease Activity (PhGADA_VAS),

Summaries will be provided by treatment arm for each post-baseline visit and Week 12 endpoint. An MMRM model, as described in Section 4.3.2. will be used to test the treatment difference of each LY dose versus placebo in change from baseline to Week 12 endpoint.

For participants who discontinue study intervention and/or receive rescue therapy, post-discontinuation or post-rescue observations will not be included.

4.4.1.2.4 HAQ-DI

Observed values at baseline and changes from baseline to Week 12 endpoint in HAQ-DI score will be summarized by treatment arm and provided as listing. An MMRM model, as described in Section 4.3.2, will be used to test the treatment difference of each LY dose versus placebo in change from baseline to Week 12 endpoint.

For participants who discontinue study intervention and/or receive rescue therapy, post-discontinuation or post-rescue observations will not be included.

4.4.1.2.5 SF-36 Domain, Component and Summary Scores

Observed values at baseline and changes from baseline to Week 12 endpoint in SF-36 summary scores will be summarized by treatment arm and provided as listing. An MMRM model, as described in Section 4.3.2, will be used to test the treatment difference of each LY dose versus placebo in change from baseline to Week 12 endpoint.

For participants who discontinue study intervention and/or receive rescue therapy, post-discontinuation or post-rescue observations will not be included.

4.4.1.2.6 SDAI

The SDAI is calculated by adding together scores from the following assessments:

- number of swollen joints (0 to 28)
- number of tender joints (0 to 28)
- CRP in mg/dL (0.1 to 10.0)

- PaGADA_VAS (0 to 100 mm), and
- PhGADA_VAS (0 to 100 mm) (Aletaha and Smolen 2005).

Observed values at baseline and changes from baseline to Week 12 endpoint in SDAI score will be summarized by treatment arm and provided as listing. An MMRM model, as described in Section 4.3.2, will be used to test the treatment difference of each LY dose versus placebo in change from baseline to Week 12 endpoint.

For participants who discontinue study intervention and/or receive rescue therapy, post-discontinuation or post-rescue observations will not be included.

4.4.1.2.7 CDAI

The CDAI is calculated by adding together scores from the following assessments:

- number of swollen joints (0 to 28)
- number of tender joints (0 to 28)
- PaGADA_VAS (0 to 100 mm), and
- PhGADA_VAS (0 to 100 mm) (Aletaha and Smolen 2005).

Observed values at baseline and changes from baseline to Week 12 endpoint in CDAI score will be summarized by treatment arm and provided as listing. An MMRM model, as described in Section 4.3.2, will be used to test the treatment difference of each LY dose versus placebo in change from baseline to Week 12 endpoint.

For participants who discontinue study intervention and/or receive rescue therapy, post-discontinuation or post-rescue observations will not be included.

4.4.1.3. Sensitivity Analysis

No sensitivity analysis will be performed.

4.4.1.4. Supplementary Analysis

No supplementary analysis will be performed.

4.4.2. Supportive Secondary Endpoints/Estimands

There is no supportive secondary endpoints/estimands.

4.5. Tertiary/Exploratory Endpoints/Estimands Analysis

4.5.1 DAS28-CRP Remission and Low Disease Activity

Remission is defined as a DAS28-CRP score of <2.6. Low disease activity is defined as a DAS28-CRP score of ≤ 3.2 .

The frequency and percentage of patients achieving remission and low disease activity will be summarized by treatment arm at each post-baseline visit. A logistic regression model will be used

to test the treatment difference of each LY dose versus placebo at each post-baseline visit with treatment group, baseline value, and previous RA therapy population as model covariates. NRI as described in Section 4.1 will be used to impute missing data for DAS28-CRP remission and low disease activity in patients who were Week 12 non-responders or who discontinued prior to Week 12.

The analyses for DAS28-CRP remission and DAS28-CRP LDA will be repeated for all visits in period 2. NRI as described in Section 4.1 will be used to impute missing data for DAS28-ESR in patients who were Week 24 non-responders or who discontinued prior to Week 24.

For participants who discontinue study intervention and/or receive rescue therapy, post-discontinuation or post-rescue observations will not be included.

4.5.2 DAS28-ESR Remission and Low Disease Activity

Remission is defined as a DAS28-ESR score of <2.6 . Low disease activity is defined as a DAS28-ESR score of ≤ 3.2 .

The frequency and percentage of patients achieving remission and low disease activity will be summarized by treatment arm at each post-baseline visit in Double-blind Treatment Period. A logistic regression model will be used to test the treatment difference of each LY dose versus placebo at each post-baseline visit with treatment group, baseline value, and previous RA therapy population as model covariates. NRI as described in Section 4.1 will be used to impute missing data for DAS28-ESR remission and low disease activity in patients who were Week 12 non-responders or who discontinued prior to Week 12.

The analyses for DAS28-ESR remission and DAS28-ESR LDA will be repeated for all visits in period 2. NRI as described in Section 4.1 will be used to impute missing data for DAS28-ESR in patients who were Week 24 non-responders or who discontinued prior to Week 24.

For participants who discontinue study intervention and/or receive rescue therapy, post-discontinuation or post-rescue observations will not be included.

4.5.3 SDAI Remission and Low Disease Activity

Remission is defined as a SDAI score of ≤ 3.3 . Low disease activity is defined as a SDAI score of ≤ 11 .

The frequency and percentage of patients achieving remission and low disease activity will be summarized by treatment arm at each post-baseline visit. A logistic regression model will be used to test the treatment difference of each LY dose versus placebo at each post-baseline visit with treatment group, baseline value, and previous RA therapy population as model covariates. NRI as described in Section 4.1 will be used to impute missing data for SDAI remission and low disease activity in patients who were Week 12 non-responders or who discontinued prior to Week 12.

The analyses for SDAI remission and SDAI LDA will be repeated for all visits in period 2. NRI as described in Section 4.1 will be used to impute missing data for SDAI in patients who were Week 24 non-responders or who discontinued prior to Week 24.

For participants who discontinue study intervention and/or receive rescue therapy, post-discontinuation or post-rescue observations will not be included.

